**Stage 2:** To accomplish Aim 2, we will randomly assign 168 undecided parents (of 84 girls & 84 boys) to 1 of 4 intervention conditions that differ by levels of cognitive processing and choice. In a 1-hour study session, parents will use a tablet-based application that directs them to either: verbalize their own arguments based on topics they choose (deep processing, high choice), verbalize arguments based on topics assigned to them (deep processing, low choice), listen to arguments based on topics they choose (shallow processing, high choice), or listen to arguments based on topics assigned to them (shallow processing, low choice). We will conduct exit interviews to assess parents' perspective on the tablet application, self-persuasion condition, and how their beliefs and experiences shape feelings about the HPV vaccine. Adolescents who accompany their parent to the study appointment at their Parkland clinic will have the opportunity to receive the 1st HPV vaccine dose from a Parkland nurse immediately after the exit interview. We will synthesize quantitative and qualitative data to select the optimal intervention condition for that will be used in Stage 3.

**Stage 3:** To accomplish Aim 3, we will recruit from pediatric neighborhood and school-based clinics, with a target of 15 parents per site (n=95). Parents will be randomly assigned to either: 1) self-persuasion plus information (optimal intervention condition from Aim 2; n=48), or 2) HPV information only (n=47). For the self-persuasion group, we will follow procedures in Stage 1. Parents in the information only group will be given a tablet and instructed to listen to information about HPV infections and the benefits and risks of the HPV vaccine. We will audiorecord the parent-provider discussion. Immediately after the visit, an RA will conduct an exit interview in which participants will be asked questions about their experiences using the tablet and their communication with the provider.

We expect to review the medical records of 369 adolescents whose parents were enrolled in our study. Medical records will be reviewed after 12 months for HPV vaccine dates. We will also abstract info for 3 other vaccines (TDAP, MCV4, & influenza) that are correlated with HPV vaccination.

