### Measurement of Primary Outcomes:

Our primary quantitative outcomes will be change in parents' HPV vaccine intentions (Aim 2) and adolescent HPV vaccine uptake (Aims 1-3). Medical records will be reviewed after 12 months to ascertain HPV vaccine status. Medical records will also be reviewed for receipt of three other adolescent vaccines (TDAP, MCV4, and influenza) as well as number and location of primary care visits in the 2 years prior to study participation.

The baseline survey will be administered to all enrolled parents (n=369) after or at the end of the recruitment call by a trained research assistant (RA), except for Aim 3 participants. The self-persuasion interview data (Aims 1A & 2), exit interviews (Aims 1-3), and audiorecorded parent-provider discussions (Aims 1B & 3) will be collected in-person by a trained RA.

Change in parents' HPV vaccine intentions (Aim 2) will be collected through the iPad application.

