## Sources of Research Material

Quantitative data will be extracted from the Parkland electronic medical record (EMR) by programmers, provided to the Principal Investigators and cleaned, recoded, and analyzed by research staff to: 1) facilitate study recruitment and 2) to assess HPV vaccine status after exposure to the intervention (Aim 3). Additional quantitative data will be collected from parent participants' responses to baseline and exit surveys (Aims 1, 2, and 3).

Qualitative data will be drawn from audio-recordings of participants' self-generated arguments (Aim 1a), audio-recordings of parent/provider interactions (Aims 1b and 3), and responses to open-ended interview questions in the exit survey after exposure to one of the 4 intervention conditions comparing levels of choice and cognitive processing (Aim 2).

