### **Analysis Plan for Aim 2:**

**Quantitative Analysis.** Data will initially be examined using univariate statistics and graphical techniques. Continuous measures will be described using medians, means, and standard deviations; dichotomous variables will be summarized as proportions. Across self-persuasion conditions, demographic characteristics will be compared at baseline via two-way ANOVA or chi-square tests, as appropriate. If groups differ on any of these variables, further analyses will be conducted both with and without these variables as covariates to determine whether these demographic variables are of relevance to group differences.

We will compare the effects of choice and cognitive processing on vaccination intentions (primary outcome) using linear regression. Independent variables will be dummy-coded variables based on two main effects (choice: high = 0, low = 1; processing: deep = 0; shallow = 1), plus their interaction. If equivalence assumptions of initial scores and parallel regression slopes for the groups are met, baseline intentions will be included as a covariate to properly model change. If not, repeated measures ANOVA will be used. We anticipate changes in intentions will be

highest in the deep processing, high choice condition, indicating an additive effect. We will also explore the interaction of the two effects. We will use a similar analytic strategy to examine the effects of choice and processing on decisional balance (secondary outcome).

**Vaccination rates.** Using eligibility data, we will assess whether vaccination rates are similar across all clinic sites.

**Qualitative Data Analysis.** We will use the same analytic process described in Aim 1b.

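### HPV vaccine uptake is listed as a primary outcome for Aim 2, but the Aim 2 analysis plan never compares the four randomised conditions on it

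*Combined protocol and SAP*

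**What the plan says.** Under Measurement of Primary Outcomes, the protocol names two primary quantitative outcomes: change in parents' intentions, assigned to Aim 2, and "adolescent HPV vaccine uptake (Aims 1-3". The same section says "Medical records will be reviewed after 12 months to ascertain HPV vaccine status". Additional Procedures for Each Stage gives the scope of that review: "We expect to review the medical records of 369 adolescents whose parents were enrolled in our study". It also describes the Aim 2 design: "we will randomly assign 168 undecided parents (of 84 girls & 84 boys) to 1 of 4 intervention conditions".

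The Analysis Plan for Aim 2 specifies two comparisons by condition. The first is "We will compare the effects of choice and cognitive processing on vaccination intentions (primary outcome) using linear regression", with choice and processing each coded 0/1 and their interaction in the model. The second is "We will use a similar analytic strategy to examine the effects of choice and processing on decisional balance (secondary outcome". The paragraph headed Vaccination rates contains only this: "Using eligibility data, we will assess whether vaccination rates are similar across all clinic sites".

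Sources of Research Material gives the post-enrolment use of the medical record as "to assess HPV vaccine status after exposure to the intervention (Aim 3". The Analysis Plan for Aim 3 is the only place where uptake is compared between randomised groups (self-persuasion v information only).

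**The concern.** An outcome listed as primary for Aim 2 has no randomised analysis in the Aim 2 plan. The vaccination analysis that is there uses clinic as the comparator and pre-enrolment data as the source, so it answers a different question.

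Aim 2 is the larger of the two randomised samples (168 v 95) and the only one that separates choice from processing. The Background states the hypothesis in terms of behaviour: self-persuasion should lead parents to opt for vaccination through one or both mechanisms. Stage 3 tests a single selected condition against information only, so it cannot show which mechanism moves vaccination. If the Aim 2 plan is followed as written, the outcome will be collected with no pre-specified use by condition. Any later comparison of uptake across the four conditions would then be post hoc, on an outcome that the protocol calls primary.

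**Working it through.** The plan gives no uptake rate, power or detectable difference for Aim 2, so there is no stated figure to reproduce. The check has two parts.

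**1. Is there a comparison of uptake by condition anywhere?**

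- *Are the data collected?* Yes. Enrolment is 53 (Aim 1a) + 53 (Aim 1b) + 168 (Aim 2) + 95 (Aim 3) = 369, the number of records to be reviewed. The Aim 2 families are therefore included.
- *Can eligibility data stand in for the outcome?* No. Criteria for Inclusion of Subjects describes them as record data on age, vaccine status and clinic site, used to establish eligibility. Table 3 requires that the series has not been started; its one exception is for Aim 1a. All 168 Aim 2 adolescents should therefore be unvaccinated in these data, with no variation for condition to explain.
- *Does the rule for choosing the optimal condition use uptake?* No. Synthesis of Quantitative and Qualitative Analyses names the effect on intentions, new concerns, difficulty and time.
- *Does a general sentence fill the gap?* No. The Aim 2 plan says that dichotomous variables will be reported as proportions, which is descriptive and names neither uptake nor condition. The synthesis paragraph mentions other outcomes but specifies no analysis of them.
- *Do the sections agree on status?* No. Measurement of Primary Outcomes makes uptake primary for all three aims. The Aim 2 plan labels only intentions as primary. Sources of Research Material mentions post-exposure vaccine status for Aim 3 only.

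**2. How precise would the missing comparison be?**

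Assumptions, none of which the documents give: equal allocation (168/4 = 42 per condition, 84 per factor level), uptake p from 20% to 50%, complete 12-month records and no clustering. The 84 girls and 84 boys in the protocol are a split by adolescent sex, not by factor level.

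The 95% half-width for a risk difference is 1.96 × √[p(1−p)(1/n₁ + 1/n₂)].

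| Contrast | n₁ v n₂ | p = 0.2 | p = 0.5 |
|---|---|---|---|
| Aim 2 marginal effect of one factor | 84 v 84 | 1.96 × √(0.32/84) = 0.121 | 1.96 × √(0.50/84) = 0.151 |
| Same, mothers only | 80 v 80 | 1.96 × √(0.32/80) = 0.124 | 1.96 × √(0.50/80) = 0.155 |
| Aim 2 simple effect | 42 v 42 | 1.96 × √(0.32/42) = 0.171 | 1.96 × √(0.50/42) = 0.214 |
| Aim 3 pilot | 48 v 47 | 0.161 | 0.201 |

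The mothers-only row uses the 160 shown for the proof-of-concept study in the Project Timeline. The timeline figures sum to 50 + 50 + 160 + 90 = 350, the number of mothers for whom the protocol says the analysis is powered.

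The coding decides which Aim 2 row applies. With both factors coded 0/1 and the interaction included, as in the Aim 2 plan, the coefficient for choice is the effect of choice within deep processing only, and the coefficient for processing is its effect within high choice only. Each is a 42 v 42 contrast. The 84 v 84 precision needs a main-effects model or effect coding.

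For scale, at an assumed two-sided 5% level, 80% power and reference uptake of 10% to 50%, 84 v 84 can detect a difference of about 17 to 22 points, and 42 v 42 about 25 to 30 points.

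**The case against.** The best defence is that the listing of uptake for Aims 1 to 3 says where records will be reviewed, not that each aim has a between-group test. Aim 1 is not randomised, so the listing cannot mean such a test there. Aim 2 is a proof of concept on mechanisms, its own plan labels only intentions as primary, and the comparison of uptake by arm is placed in Aim 3. This reading is plausible, and part of it stands: the sponsor may never have intended uptake as a confirmatory endpoint for Aim 2. It does not remove the conflict, because Measurement of Primary Outcomes gives uptake that status without qualification.

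Three stronger readings are tempting, but the documents do not support them.

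- A reader might infer that Stage 2 is decided on intentions alone. It is not. The synthesis rule also rejects a condition that raises new concerns for many participants, is difficult or takes significant time, and decisional balance is analysed by condition.
- A reader might infer that Sources of Research Material restricts 12-month follow-up to Aim 3. That section is a list of data sources and is contradicted by the plan to review all 369 records. It is an inconsistency, not a limit on the data.
- A reader might infer that Aim 2 would estimate uptake effects more precisely than the pilot. This holds for marginal contrasts (12 to 15 points v 16 to 20) but not for simple effects under the plan's coding (17 to 21). The contrasts also differ: Aim 2 compares four active conditions, and the pilot compares self-persuasion with information only.

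It is also fair to object that 12-month data may arrive after the Stage 3 condition has been chosen. The added analysis should therefore not be presented as an input to that choice.

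**Conclusion.** The point holds as a conflict between sections together with a missing analysis. Uptake is declared primary for Aim 2 and will be collected on all 168 families, yet no section compares the randomised conditions on it. The clinic-site check cannot substitute for that comparison.

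The remedy has a modest yield. A marginal comparison would carry a half-width of about 12 to 15 points (slightly wider for mothers only) and simple effects about 17 to 21, given equal allocation, uptake of 20% to 50%, complete records and no clustering. This supports estimation, not a confirmatory test, and only large differences would be evident. The value lies in reporting Aim 2 fully and in informing the later efficacy trial; it would not change how Stage 2 selects a condition. The change should be made, but the Aim 2 analysis of intentions does not depend on it.

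**What to change.** 1. In the Analysis Plan for Aim 2, under Vaccination rates, add 12-month 1-dose and 3-dose uptake by randomised choice and by randomised processing. Report marginal risk differences with 95% confidence intervals, from a main-effects model or with effect coding. Explore the interaction separately. The clinic-site check can stay as a description of the sites.
2. State that this analysis is estimation, secondary to intentions, reported when the 12-month data mature and not used to select the Stage 3 condition.
3. Amend Measurement of Primary Outcomes so that the status of uptake in Aim 2 matches item 2, and extend Sources of Research Material so that post-exposure vaccine status is no longer tied to Aim 3 alone.
4. State the Aim 2 allocation ratio and whether this analysis covers all parents or mothers only, since the precision depends on both.

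The cost is one extra analysis of data already planned for collection, plus edits to three sections. The downside is that intervals this wide can show only large differences, and the report should say so.

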During the study appointment, a bilingual RA will 1) obtain HIPAA authorization to review the adolescent patient's EMR, and 2) instruct the participant on how to use either the English or Spanish version of the tablet application. For Aims 1a and 2, the study appointment will last about 60 minutes and will be audio-recorded. For Aims 1b and 3, pre-clinic visit study activities will take 10-20 minutes; post-visit activities will take another 20-25 minutes. All study staff will be trained by Drs. [name] and [name]. Parent participants will receive a \$50 honorarium in the form of a gift card.

We will conduct study visits with a total of 369 parent participants. We expect very few parents will be fathers (<5%; n = 19) and have powered our analysis to only analyze data from mothers of adolescent patients (n = 350). For Aim 1, we will enroll 106 parents: 53 for formative research on self-generated arguments (Aim 1a), and 53 to characterize parent-provider discussions about the HPV vaccine (Aim 1b). For Aim 2, 168 parents will be enrolled for self-persuasion intervention conditions comparing levels of choice and cognitive processing. We will enroll 95 parents for Aim 3, recording provider/patient interaction and testing of tablet-based application. We expect to enroll 18 providers in order to audiorecord the parent-provider discussions for Aims 1b and 3.

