### Project Timeline

Project Timeline	Year 1				Year 2				Year 3				Year 4				Year 5			
	Q1	Q2	Q3	Q4																
IRB & staff training																				
Advisory Committee meetings																				
Meetings with communication consultant, [name]																				
Build study database & CATI software for surveys																				
Build, pretest, refine, & tech support for the self-persuasion tablet																				
Use EMR to identify eligible patients for each stage																				
Stage 1: Define intervention content (Aim 1)																				
Conduct cognitive interviews of self-generated arguments (n=50)																				
Transcribe recordings and code interview data																				
Clinic launch meeting for recording discussions																				
Recruit & audiorecord parent-provider discussions (n=50)																				
Apply [name]'s coding scheme to transcribed data on discussions																				
Stage 2: Optimize intervention's effects (Aim 2)																				
Refine tablet program for 4 self-persuasion intervention conditions																				
Recruit & conduct proof of concept study (n = 160)																				
Analyze & synthesize quantitative and qualitative data																				
Select self-persuasion intervention condition for Stage 3																				
Stage 3: Assess feasibility in safety-net clinics (Aim 3)																				
Clinic launch meeting for pilot RCT																				
Conduct pilot including audiorecord discussions (n =90)																				
Code parent-provider discussions																				
Analyze data & publish manuscripts																				

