**Synthesis of Quantitative and Qualitative Analyses.** To determine which self-persuasion condition (1, 2, or 3) is optimal for our safety-net population and will be tested in Stage 3, we will triangulate quantitative and qualitative findings by creating a summary profile for each condition. The optimal condition will be one that has a positive effect on intentions, but also minimizes participants' negative reactions to using the tablet application. A condition that does not affect intentions will not be considered optimal, regardless of its effect on other quantitative and qualitative outcomes. Likewise, a condition that affects intentions but for many participants raises new concerns, is rated as difficult to complete, or takes significant time to complete will not be considered optimal. Drs. [name] and [name] will jointly make this decision in consultation with the team.

**At the end of Stage 2, we will have quantitative and qualitative data that clarify whether it is best to ask parents to verbalize their own arguments, to choose argument topics they prefer, or both, and which self-persuasion condition is optimal in our underserved, safety-net population.** Evidence clarifying which of the two specific mechanisms (deep processing, choice) has an effect, or whether they have an additive effect, will be critical to how we select the optimal self-persuasion condition to implement in Stage 3. For example, if there is an effect of processing but not choice, we would use Condition 2 that has parents verbalize arguments based on assigned topics that are most persuasive rather than allowing them to generate arguments based on chosen topics that may be less persuasive. If there is an effect of choice but not processing, we would use Condition 3 that has parents choose argument topics they want to hear rather than having them go through the more taxing process of generating their own. If both have an effect, Condition 1 will be selected for Stage 3.

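### The example branches for choosing the Stage 3 condition use yes/no main-effect verdicts and leave out the fitted interaction, and a highest Condition 1 is read as proof of additivity

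*Combined protocol and SAP*

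**What the plan says.** The Stage 2 design is a 2×2 factorial: "we will randomly assign 168 undecided parents (of 84 girls & 84 boys) to 1 of 4 intervention conditions". Condition 1 combines deep processing with high choice, Condition 2 is deep with assigned topics, and Condition 3 is listening with chosen topics. By elimination, Condition 4 is listening with assigned topics.

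Analysis Plan for Aim 2, Quantitative Analysis, specifies a linear regression of intentions on "dummy-coded variables based on two main effects (choice: high = 0, low = 1; processing: deep = 0; shallow = 1), plus their interaction". It expects the change to be "highest in the deep processing, high choice condition, indicating an additive effect", and says the interaction will be explored.

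The Synthesis of Quantitative and Qualitative Analyses section restricts the candidates to Conditions 1 to 3. It then illustrates the choice with three branches. Processing without choice leads to Condition 2. For choice without processing, "If there is an effect of choice but not processing, we would use Condition 3". For the third, "If both have an effect, Condition 1 will be selected for Stage 3". The section also sets a floor: "A condition that does not affect intentions will not be considered optimal". Findings are triangulated with qualitative data, burdensome conditions are ruled out, and two investigators decide with the team.

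**The concern.** The branches need only two verdicts, one per mechanism, and that is enough only if the mechanisms add. If they interact, the main effects do not describe the individual conditions, and the quantity that would reveal this is fitted but enters no branch. The inference in the analysis plan has the same weakness: additive and synergistic effects both put Condition 1 on top, so its rank cannot tell them apart.

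The wording also leaves open which main effect is meant. With 0/1 coding and an interaction in the model, each main-effect coefficient is a simple effect against Condition 1, not an average over the other factor. The two readings can give different verdicts from the same data.

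The selected condition is the only active intervention in Stage 3, whose estimates are meant to guide the later efficacy trial. Whether the mechanisms add is also the main scientific conclusion of Stage 2.

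**Working it through.** **1. Inputs.** The protocol randomises 168 parents, so 168/4 = 42 per cell. The Project Timeline gives "Recruit & conduct proof of concept study (n = 160"), so 160/4 = 40 per cell. The counts fit: 53+53+168+95 = 369 enrolled; 369−19 fathers = 350; and 50+50+160+90 = 350 in the timeline. I therefore read 160 as the mothers analysed. The protocol says the investigators "have powered our analysis to only analyze data from mothers of adolescent patients (n = 350"), but gives no power, alpha, SD or effect size for Aim 2, so there is no figure of its own to reproduce. The d = 0.60 in the Background is for self-written arguments on exercise intentions, not for choice or processing alone.

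Assumptions: 40 per cell, residual SD 1, two-sided 0.05 counted only in the favourable direction, no covariate gain.

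**2. Contrasts.** Let m1 to m4 be the condition means.

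- Averaged processing effect: (m1+m2)/2 − (m3+m4)/2. Averaged choice effect: (m1+m3)/2 − (m2+m4)/2. SE of each = 1/√40 = 0.158.
- As coded (reference cell Condition 1): choice coefficient m2 − m1, processing coefficient m3 − m1. SE of each = √(2/40) = 0.224.
- Interaction: m1 − m2 − m3 + m4. SE = 2/√40 = 0.316.

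**3. Why rank and main effects cannot show additivity.** Compare two truths, with Condition 4 set to 0:

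| Truth | m1, m2, m3, m4 | Averaged effects | Coded effects (size) | Interaction |
|---|---|---|---|---|
| Additive, 0.3 each | 0.6, 0.3, 0.3, 0 | 0.3, 0.3 | 0.3, 0.3 | 0 |
| Only the combination works | 0.6, 0, 0, 0 | 0.3, 0.3 | 0.6, 0.6 | 0.6 |

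Condition 1 is highest, by the same 0.6 SD over Condition 4, in both rows, and the averaged main effects are identical. In the second row Conditions 2 and 3 do nothing.

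**4. The branches applied mechanically.** I drew four cell means and a pooled variance (156 df), tested both mechanisms and followed the three branches. Results are the percentage of trials choosing Condition 1 / Condition 2 or 3 / reaching no branch:

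| Truth | Averaged main effects | 0/1-coded coefficients |
|---|---|---|
| Additive, 0.4 SD each | 51 / 41 / 8 | 26 / 33 / 41 |
| Additive, 0.6 SD each | 93 / 7 / 0 | 63 / 25 / 12 |
| Only the combination, 0.6 SD | 22 / 50 / 28 | 63 / 25 / 12 |

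In the last row the middle figure is the chance of choosing a condition with zero benefit. The coding cuts both ways: it lowers the chance of choosing Condition 1 under additivity and raises it when only the combination works.

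**5. Sensitivity.** A baseline correlation of 0.5 raises the additive 0.6 SD results for Condition 1 to 98% (averaged) and 78% (coded). Using 42 rather than 40 per cell improves results by 0 to 4 points.

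**6. Is taking the highest mean a safe substitute?** No. With no true effect the four means are exchangeable, so Condition 4 is highest in 1/4 of trials and some candidate exceeds it in 1 − 1/4 = 75%. The branches would advance a condition in about 5%.

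**The case against.** The strongest reply is that the branches are introduced as examples within a mixed-methods decision, and no significance test is attached to the word effect. The percentages therefore describe an algorithm that the protocol does not state. Reaching no branch in the simulation means only that no example applied. This stands, and it limits what the figures can show.

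A reader might infer that the plan will often carry forward the wrong condition or none. The documents do not support that. With averaged additive effects of 0.6 SD, Condition 1 is missed in only 7% of trials, and conditional baseline adjustment would lower that. In the additive cases Conditions 2 and 3 still beat Condition 4 by one full mechanism effect. The protocol also gives reasons for preferring a simpler task: assigned topics may be more persuasive, and generating arguments is more demanding.

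Nor is the interaction ignored outright. It is in the model and will be explored, and the synthesis section says that whether the effects add matters for selection. The gap is confined to the branches and to the inference from Condition 1's rank.

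It is also tempting to say that the criterion has no comparator, so that a before-after rise would let every condition pass. The restriction to Conditions 1 to 3 and the between-condition regression both imply Condition 4 as the reference. The plan would be clearer if it said so. The absence of a threshold and of an action when neither effect is seen is missing detail, not a separate error.

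Finally, the branches do guard against needless burden. If only processing works (0.4 SD), averaged main effects lead to Condition 1 in 2% of trials; taking the highest mean would do so in about 49%.

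**Conclusion.** The concern holds in a limited form. The example branches use yes/no verdicts on two main effects and omit the interaction, and the analysis plan accepts as evidence of additivity a pattern that synergy also produces. Both can change which condition goes forward and what Stage 2 concludes.

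The size depends on quantities the documents do not give. Under the stated assumptions, mechanical use of the branches finds an additive best Condition 1 in 51% to 93% of trials for 0.4 to 0.6 SD with averaged effects, and in 26% to 63% with the coefficients as coded. In the combination-only case a zero-benefit condition is chosen in 50% or 25%. The spread between the two readings is itself a reason to specify the contrast. None of this is an error rate for the investigators' full decision.

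**What to change.** In the Synthesis section:

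- Base the quantitative input on the baseline-adjusted differences of Conditions 1, 2 and 3 from Condition 4, each with a 95% CI, from the model that includes the interaction.
- Count a condition as having a favourable effect on intentions only if that randomised difference meets a stated evidential threshold; exceeding zero is not enough.
- Use the main-effect branches only when the interaction estimate and its CI are compatible with additivity. Otherwise choose from the condition-level differences together with the burden criteria already listed.
- State the action if no condition meets the threshold.

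In the Quantitative Analysis section, claim additivity only from the interaction estimate and its CI, and say that main effects are averaged contrasts (for example through −1/+1 coding).

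Do not mandate picking the highest mean, for the reason in step 6 of the working.

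The cost is wording and a little more analysis. Condition-level differences are less precise than averaged main effects (SE 0.224 against 0.158 SD). The interaction is less precise still: its 95% CI is about ±0.62 SD (1.975 × 0.316). The plan should therefore say in advance how large an interaction would count against additivity, and should not treat a non-significant interaction as proof of it.
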